To maximize the chances of a successful TESE, spermatogenesis should already be underway, for which the production of testosterone is crucial. However, testosterone is also responsible for (irreversible) virilization, such as deepening of the voice and facial hair growth. Therefore, it is highly burdensome for this group of patients to postpone puberty suppression in order to secure their fertility for the future, especially considering that active fertility desire does not exist at the start of puberty.

Currently, there is a lack of valid clinical factors to predict when spermatogenesis has sufficiently progressed in transfeminine adolescents. The intratesticular testosterone level is significantly higher than the peripheral blood testosterone level, and the blood testosterone value is not determinative of the intratesticular level. Ideally, a high intratesticular testosterone level would be beneficial for

sperm production, while maintaining the lowest possible peripheral testosterone level to minimize virilization.

In the current clinical practice, the child endocrinologist determines the Tanner stage before initiating puberty suppression, followed by fertility counseling with the gynecologist. If fertility preservation is desired afterward, a referral to the andrologist is made to assess the indication for TESE and determine the optimal timing for the procedure. In cases where ejaculation is not possible, the andrologist uses ultrasound measurements of testicular volume, serum testosterone, LH, and FSH levels to make this determination. Recent Australian research in transfeminine adolescents has shown that testicular volume appears to be the most predictive factor. This finding is based on a retrospective cohort study with a small sample size of N=31 (11).

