| Study design | 
For part 1 of the research question "when is the sperm yield from TESE most successful," the study design is observational, including both retrospective and prospective cohort research, utilizing data from medical records.
 
To address the second part of the research question, we intend to employ a descriptive research method. This will involve qualitative research through interviews and quantitative research through questionnaires administered to both the children and their parents during or after the treatment.
 |
| Study population | 
Healthy adolescents assigned male at birth with gender dysphoria and a desire for surgical fertility preservation prior to or after the
 |

| | |
|------------------------------------|--|
| | temporary discontinuation of puberty suppression, who have been referred to the andrologist |
| Inclusion criteria | 
Patients will be included if they meet the following criteria:
 
 • (Parents of) Individuals assigned male at birth who identify as transfeminine (trans girl, non-binary person, etc.). • Under the care of a specialized gender center or clinic • Have a diagnosis of gender dysphoria according to the Diagnostic and Statistical Manual of Mental Disorders, Fifth Edition (DSM-5) or a diagnosis of gender incongruence according to the International Classification of Diseases, 11th Revision (ICD-11). • Have not yet started or have discontinued puberty suppression before the start of gender affirming hormone treatment. • Referred or scheduled for referral to the andrologist following fertility counseling. |
| Exclusion criteria | Patients will be excluded if they do not wish to participate in this research. |
| Sample size | We aim to conduct the study over a period of 2 years to include a sufficient number of 30-40 adolescents, allowing us to generate valid data. |

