| Standard care / Standard treatment | All adolescents are referred for fertility counseling before starting puberty suppressants. In this consultation, a counseling session takes place regarding fertility preservation. If the patient expresses a desire for preservation and is eligible for TESE (due to age/early puberty/incapacity to produce ejaculation), they are referred to the andrologist. An intake appointment is scheduled, after which the indication for TESE is confirmed. Currently, the indication is based on blood values (testosterone, LH, FSH) and an ultrasound to determine testicular volume. If the testicular volume or laboratory values are still insufficiently indicative of a successful TESE, the examination is repeated after 3 to 6 months or upon the patient's request if puberty progresses more rapidly and intensely than expected, thus tailored to the patient. The TESE procedure is performed in an outpatient setting under general anesthesia with local anesthesia, using microsurgery |

| | |
|-----------------------------|---|
| | techniques to obtain small pieces of testicular tissue, ensuring reversibility of the procedure. |
| Study parameters | 
Primary outcome measures:
 
Part 1:
 
Ultrasound-determined testicular volumes before TESE procedure, when this is not available, we will use the measurements of the Tanner stage at the time of the procedure, by the pediatric endocrinologist.
 
Laboratory values (testosterone, LH, FSH) shortest before the TESE procedure, including subsequent measurements, collected as part of routine clinical care for non-study purposes
 
Age at the time of TESE
 
Presence of spermatozoa
 
Number of cryopreserved straws
 
Quality of obtained sperm cells (concentration/motility)
 
Part 2:
 
Experience of the TESE procedure for the patient and parents
 
Experience of counseling for the patient and parents
 
Experience of any waiting period for the patient and parents
 
Feasibility for adolescents: Outcome of TESE after referral (whether the TESE procedure was carried out or not)
 |
| Study endpoints | 
Secondary outcome measures:
 
Progression of secondary sexual characteristics/virilization from the time of referral to the TESE procedure
 
Subgroup of patients who temporarily discontinued puberty suppressants
 |

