| Statistical analysis | 
The statistical program SPSS will be used for analyzing the observational cohort and questionnaires.
 
Descriptive analyses will be conducted to display the central tendency (mean, median, and mode) and variation (range and standard deviation) of the included sample.
 |

| | |
|--|---|
| | 
To demonstrate a statistically significant relationship between different variables and the observed outcomes, linear and multivariate regression analyses will be employed. If necessary, adjustments will be made for confounding factors.
 
The questionnaires will be sent via Castor and analyzed using SPSS.
 
The interviews will be transcribed verbatim. Transcripts will be coded using the MaxQDA software program, from which thematic analysis themes will be derived.
 |
| Burden for the participant | 
The interviews are conducted face-to-face or, in the case of long travel distances, through video consultations. The interviews last for a single session of 45-60 minutes. The questionnaires are sent online and take approximately 15 to 20 minutes to complete. The topics of fertility and the physical changes related to the TESE procedure discussed in the interviews can be considered intimate information. However, it is important to note that these topics are also routinely discussed by physicians and psychologists during clinical visits. Therefore, participants may find it relatively normal to discuss these topics with their healthcare providers. Nevertheless, participants have the option to select "I do not want to complete this questionnaire" for each questionnaire, in which case the questions will be removed from the digital survey. Apart from the time invested in completing the questionnaires and/or participating in interviews, there is no additional burden on the participants. Blood tests are always part of the treatment process and there are no additional blood sampling moments.
 |
| Risk for the participant | The participant faces no risks. |
| Benefits of participating in the research | The participant does not have direct benefits from participating in the research. Indirect benefits may include the potential improvement of care and information provision within the Knowledge and Care Center for Gender Dysphoria, both nationally and internationally, based on the research outcomes. This can be perceived as highly meaningful. |

| | |
|---|---|

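### Objective 1 is about prediction, but the protocol plans significance testing by multivariate regression; with five markers and at most 30-40 adolescents, a joint fit would overstate accuracy and could hide a useful marker

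*Protocol*

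**What the plan says.** The Objective section of the Protocol gives the first aim as finding non-invasive clinical parameters that point to a high likelihood of mature sperm. The background text adds that the cohort should allow better prediction in future patients.

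The Statistical analysis section states: "To demonstrate a statistically significant relationship between different variables and the observed outcomes, linear and multivariate regression analyses will be employed". It continues: "If necessary, adjustments will be made for confounding factors". No confounders are named.

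The Study parameters section lists five candidate markers for Part 1: "Ultrasound-determined testicular volumes before TESE procedure" (Tanner stage where no ultrasound is available), "Laboratory values (testosterone, LH, FSH) shortest before the TESE procedure", and age at TESE. The yield outcomes include presence of spermatozoa, which is a yes/no result.

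The Sample size section aims for a "sufficient number of 30-40 adolescents" over two years, with no effect size, power or precision behind the figure. Under Part 2, whether TESE took place after referral is itself an outcome, so the number with a sperm result may be below 30-40.

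The background text reports from a retrospective cohort of 31 that "testicular volume appears to be the most predictive factor".

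**The concern.** The stated analysis target does not match the objective. A coefficient adjusted for the other markers tells whether a marker adds information beyond them. Objective 1 asks whether the marker predicts sperm. When markers share information, as puberty markers plausibly do, a marker can predict well alone and still be non-significant after adjustment. Confounding is a causal idea and does not decide whether a parameter is a useful predictor.

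The sample is also small for a joint model of five markers. An unpenalised fit adapts to chance features of the data and then looks more accurate than it will be in the next patients.

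Either result would bear on the advice the study is meant to improve. A useful marker might be reported as not significant, or a combined model might be reported with accuracy that is not reproduced. The Protocol itself describes the burden of both an early procedure without sperm and a long wait.

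**Working it through.** **The plan's own figure.** The 30-40 comes with no inputs, so there is nothing to reproduce.

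**Inputs from the Protocol.** Five markers; 30-40 adolescents; a yes/no sperm result.

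**Assumed inputs (not in the documents).** Share in the smaller outcome class 30-50%; common correlation r between markers 0.3-0.8; two-sided 5% tests; only one marker truly related to the outcome. Confounders are left out, which favours the plan.

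**Step 1: events per marker** = n × (share in smaller class) / 5.
- 30%: 30 × 0.3 / 5 = 1.8; 40 × 0.3 / 5 = 2.4.
- 50%: 30 × 0.5 / 5 = 3.0; 40 × 0.5 / 5 = 4.0.
- If only 20 have a TESE result: 20 × 0.3 / 5 = 1.2 to 20 × 0.5 / 5 = 2.0.

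**Step 2: variance inflation** for five equally correlated markers, VIF = (1 + 3r) / ((1 − r)(1 + 4r)).
- r = 0.3: 1.9 / (0.7 × 2.2) = 1.23.
- r = 0.5: 2.5 / (0.5 × 3.0) = 1.67.
- r = 0.8: 3.4 / (0.2 × 4.2) = 4.05.

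The penalty for adjustment is therefore mild at low correlation and heavy at high correlation.

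**Step 3: power for the one true marker.** Logistic simulation with 60% success, log odds ratio 1.2 or 1.8 per SD (odds ratio 3.3 or 6.0), n = 30 and 40, likelihood-ratio tests. Ranges run over both effects and both sample sizes.

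| Analysis | Chance that the true marker is significant |
|---|---|
| Tested alone | 77-100% |
| With the other four, r = 0.3 | 71-97% |
| With the other four, r = 0.6 | 51-85% |
| With the other four, r = 0.8 | 35-60% |

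With a weaker effect (log odds ratio 1.0, 50% success) and r = 0.8, the joint figures are 27% at n = 30 and 32% at n = 40, against 66% and 82% alone.

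**Step 4: accuracy of the joint fit.** In the setting of Step 3, the apparent AUC of the five-marker model exceeds its AUC in new patients by about 0.07-0.15 at every r from 0.3 to 0.8. At r = 0.6-0.8 the apparent AUC is 0.83-0.89 and the AUC in new patients 0.70-0.81. The true marker alone gives 0.77-0.85, with apparent and true values about equal. With the weaker effect, the apparent AUC is 0.80-0.82 against 0.66-0.69 in new patients.

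**Step 5: linear regression, which the Protocol names.** With a continuous outcome and true R² 0.25, apparent R² is 0.33-0.37 and R² in new patients 0.05-0.12. At r = 0.8 the true marker is significant in 29% (n = 30) and 37% (n = 40) of studies jointly, against 83% and 92% alone. The problem is therefore not tied to the type of regression.

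**The case against.** The strongest reply is that the Protocol never commits to a five-marker model. It does not say that all markers enter together, gives no rule for dropping non-significant ones, and makes adjustment conditional. The pairing of linear with multivariate regression can be read as one-marker models followed by joint ones, so the single-marker analysis may already be intended. No accuracy measure is promised. Shrinkage, covariate limits and internal validation are commonly left to an SAP, so their absence here is no fault. All of this stands, and it makes the harm conditional on how the sentence is carried out.

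The correlations are also assumed, and there are reasons why they might be weaker. The cohort admits patients who interrupted puberty suppression. Selection for TESE rests on volume and hormone values, which may narrow their range. The Protocol itself says that puberty runs differently in each individual. The 60% success rate and the single true marker are assumptions too, and the latter makes the other four markers useless by design.

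A reader might infer that the planned analysis will usually discard the useful marker. The figures do not support that: at r = 0.3 the marker is kept in 71-97% of studies and at r = 0.6 in 51-85%. It is lost in about half or more only at high correlation or with a weaker effect. A reader might also infer that all adjustment should be barred, or that volume should be the sole primary marker. Neither follows. Whether a marker adds information is a fair second question, interrupted suppression is a named subgroup, and the support for volume is one retrospective study of 31.

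What the reply does not remove is the wording of the Protocol. Its stated aim is to demonstrate significance, and that is not the aim of Objective 1.

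**Conclusion.** The point holds as a mismatch between objective and analysis, with a conditional consequence. If the five markers are fitted jointly without penalisation in 30-40 adolescents, there are about 2-4 events per marker and the apparent AUC is about 0.07-0.15 too high. That overstatement appears at every correlation examined, so it does not depend on the markers being strongly related.

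Loss of the useful marker does depend on it: power is about 71-97% at correlation 0.3 and 35-60% at 0.8, against 77-100% alone. This is a risk of the stated approach, not its expected result.

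The sizes rest on an assumed success rate, assumed effects, equal correlations and one true marker. If fewer than 30 adolescents reach TESE, there are fewer events per marker still. The change is worth making because the sentence as written points the analyst to the wrong criterion and the correction is cheap.

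**What to change.** In the Statistical analysis section, state the following for Objective 1.

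- The main result is the relation of each marker, taken singly, to presence of spermatozoa, with a confidence interval. Testicular volume is listed first, as the marker the background points to. Patients with a Tanner stage in place of ultrasound volume are analysed separately.
- Any joint model is limited to very few markers, fitted with Firth or ridge shrinkage, and reported with bootstrap optimism-corrected accuracy.
- Significance after adjustment is not used to decide whether a marker predicts. Prior puberty suppression may still be examined as the subgroup the Protocol names.

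The cost is a few sentences and slightly more analysis work, with no new data or participants. The price is that the study makes no claim about independent effects of all five markers.
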